2.2 Secondary Outcomes

We will also assess intervention efficacy on a panel of self-reported outcomes including condomless anal intercourse (CAI), STI infections, and disclosure behaviors, intentions and self-efficacy. For binary outcomes, we define intervention efficacy as a difference in proportions, while for continuous outcomes, we define efficacy as a difference in means. (See Table 2 on page 45)

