4.0 SELECTION AND ENROLLMENT OF PARTICIPANTS

4.1 Inclusion Criteria

Inclusion Criteria for All Aims

- Age 16-29 years
- Assigned male sex at birth
- Born male and male-identified
- Able to understand, read, and speak English

Additional Criteria for Technical Pilot:

- Reports ≥ 1 episode of CAI with a male partner in past 6 months
- HIV-positive (self-report)

Additional Criteria for RCT:

- HIV-positive (medical chart review)
- Viral Load measure within 12 months of screening date (assessed by chart review, blood draw, or shared by participant via video teleconferencing or Qualtrics)
- Owns and has reliable access to a smartphone or tablet
- Has reliable internet access
- Reports ≥1 episode of anal sex with a male partner in past 6 months (self-report) OR reports STI diagnosis (urethral/rectal gonorrhea or chlamydia or syphilis) in the last six months (self-report OR medical chart review)

As this is a minimal risk study, we will seek a waiver of parental consent for YMSM under age 18 (see Human Subjects section).

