5.0 STUDY PROCEDURES

5.1 Enrollment Procedures

Technical Pilot

We will enroll 8-16 participants. The technical pilot only consists of one in-person session. After being consented, all participants will be given brief instructions on the purpose of Tough Talks and an overview of how to use the program. They will complete an online assessment at baseline and a paper assessment at the end of using the program. Participants will also be asked to provide feedback during

interviews conducted by study staff about intervention content, technical performance, errors and bugs encountered, overall experiences using Tough Talks, and feedback for further refinement. Participants will receive \$75 for participation.

RCT

We will enroll a total of 198 participants. Study staff will review the consent in person or over Zoom (or another HIPPA compliant system) and if the participant decides to enroll, he can sign the paper copy or electronic copy programmed in Qualtrics. After participants are consented, they will complete the baseline web-based CASI survey using Qualtrics software and then be randomized into the Tough Talks online/at-home intervention (Arm 1), the Tough Talks clinic-based intervention (Arm 2) or the SOC control condition (Arm 3). At this visit, those randomized to the online intervention (Arm 1) will download the Tough Talks app onto their personal mobile phone or tablet, have their unique App ID recorded by study staff, set up their preferred email login and password information, and receive information on how to contact study personnel for any technical issues. Arm 1 participants will have access to all of the intervention features upon download. Participants randomized into this arm are expected to proceed through the entire intervention within 30 days. Arm 1 participants who have not completed the app around 2 weeks after enrollment, around 3 weeks after enrollment, and during week after enrollment will be reminded via text or email via SMART to use the Tough Talks app.

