6.5 Three-Month Assessment

A second assessment should occur 90 days (3 months) after study enrollment. However, the assessment may occur 15 days prior to or 30 days after the ideal three-month assessment time point. SMART will aid study staff in ensuring retention. SMART maintains participant follow-up timelines, tracks participant communications, and automates sending of e-mail, text reminders, and calendar invites to participants for follow-up survey and visit completion. At three months, all participants will complete a second online survey and staff will conduct a medical chart abstraction for VL results in the week window surrounding the three-month follow up visit (both before and after). Participants will complete the 3-month follow up survey remotely and will receive \$25 for completion. Payment is not contingent upon having a VL result in the required window. Participants who miss their 1-month follow up are eligible to complete their 3-month visit.

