10.1.3 RCT

Conduct a combined efficacy/effectiveness trial to compare the intervention delivered online, in the clinic, or SOC clinic disclosure messaging. The primary outcome of HIV viral suppression will be assessed at six months. We will also assess intervention efficacy on a panel of self-reported outcomes including CAI, STI infections, disclosure behaviors, intentions and self-efficacy assessed at baseline, 3 months, and 6 months. Cost effectiveness of both intervention arms will also be assessed.

The primary analysis will be based on intention-to-treat principles, where all participants are assumed to have followed their randomized assignment; secondary analyses will account for observed intervention completion. Additionally, we will develop a mathematical model to estimate secondary HIV transmissions and potential transmissions averted as a result of the intervention's effect on viral suppression and CAI with susceptible partners.

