12.0 PUBLICATION OF RESEARCH FINDINGS

Any presentation, abstract, or manuscript will be made available for review by the study sponsor(s) prior to submission.

Schedule of Events

Table 2: Schedule of Study Evaluations and Outcomes						
			BL	One-month	Three-months	Six-Months
Primary Outcomes						
Viral load suppression	Viral load suppression will be defined as HIV RNA < lower limit of detection as per the laboratory at each clinical site.	Medical Chart review or blood draw for study	X		X	X
Secondary Outcomes						
Condomless anal sex (CA) with potentially susceptible partner	≥1 act of CAI with a partner who is not known to be HIV-positive in the last 3 months.	CASI	X		X	X
Disclosure Self-Regulation (Behaviors)	Measure of desire and actual disclosure behaviors to family, peers and sex partners	CASI	X	X	X	X
Self-efficacy to disclose	Adapted version of disclosure self-efficacy measure for MSM (6 items) ¹⁴ .	CASI	X	X	X	X

Disclosure outcome expectations	Adapted version of disclosure outcome expectations measure for MSM (2 domains: self-evaluative expectancies - 6 items, and hedonistic outcome expectancies – 3 items) ¹⁴ .	CASI	X	X	X	X
Intentions to disclose	Adapted version of disclosure intentions measure for MSM (1 item) ¹⁴ .	CASI	X	X	X	X
Consequences of disclosure	Measure indicating how important each of a list of possible consequences concerning disclosure was to them when considering disclosing to a specific person ²⁹ .	CASI	X	X	X	X
Potential Moderators						
Brief Symptom Inventory (BSI)	The BSI yields nine primary symptom scales and global indices and has norms for adolescents and adults ³⁰ .	CASI	X		X	X
The Alcohol, Smoking, and Substance Involvement Screening Test (ASSIST)	Individuals respond to eight items assessing the frequency and consequences of drug and alcohol use ³¹ .	CASI	X		X	X
Other Outcomes of Interest						
Retention in Care	# missed and scheduled visits over last 6 months	CASI	X		X	X
STIs	New diagnosis of rectal/urethral gonorrhea or chlamydia or syphilis in last 6 months.	Medical Chart abstraction CASI	X		X	X
Adherence	A visual analogue scale (VAS) will be used to assess antiretroviral therapy adherence over the last 3 months ³² .	CASI	X		X	X
PrEP uptake in serodiscordant partners	Participants will be asked to report on any known PrEP use among their serodiscordant partners.	CASI	X		X	X
Feasibility/Acceptability and Cost						

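### STI and retention-in-care outcomes look back six months at the three-month visit, so 33-58% of the window precedes randomisation

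*Combined protocol and SAP*

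**What the plan says.** Table 2 in the Schedule of Events defines the STI outcome as "New diagnosis of rectal/urethral gonorrhea or chlamydia or syphilis in last 6 months", taken from chart abstraction and the self-administered survey (CASI). Retention in care is the number of "missed and scheduled visits over last 6 months", taken from CASI only. Both are marked at baseline, three months and six months. In the same table, condomless anal intercourse (CAI) and antiretroviral adherence use a three-month look-back.

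On timing, section 6.5 states: "A second assessment should occur 90 days (3 months) after study enrollment". It adds that "the assessment may occur 15 days prior to or 30 days after the ideal three-month assessment time point". Section 5.1 puts randomisation at the enrolment visit: participants "complete the baseline web-based CASI survey using Qualtrics software and then be randomized".

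On entry, section 4.1 accepts a participant who "reports STI diagnosis (urethral/rectal gonorrhea or chlamydia or syphilis) in the last six months", as an alternative to a recent episode of anal sex.

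On status, section 2.2 says efficacy will be assessed on outcomes that include "condomless anal intercourse (CAI), STI infections, and disclosure behaviors, intentions and self-efficacy", and section 10.1.3 describes a "panel of self-reported outcomes including CAI, STI infections, disclosure behaviors, intentions and self-efficacy assessed at baseline, 3 months, and 6 months". Table 2 nevertheless lists STIs and retention under Other Outcomes of Interest. No section limits the three-month count to events after randomisation, or says what makes a diagnosis new.

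**The concern.** A six-month recall period asked about three months after randomisation covers the three months before it as well. Events in that earlier stretch cannot depend on the assigned arm. They add the same expected amount to every arm and blur whatever difference arose afterwards.

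For STIs the entry rule makes this sharper. A diagnosis in the 90 days before enrolment can qualify a participant, be recorded at baseline, and be recorded again as new at a day-90 visit.

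The pattern looks unintended. CAI and adherence use windows that match the visit spacing, and the transmission model (section 10.3.3, RCT Secondary Analysis Plan) divides time into separate three-month intervals on either side of baseline. At stake is whether any three-month between-arm estimate for STIs or retention can be read as an effect of the intervention over its first three months.

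**Working it through.** **The plan's own figure.** The plan states no rate, effect size or power for STIs or retention. Its only sample-size figure, in section 10.2.3, is 66 per arm for viral suppression (0.66 v 0.88, two-sided alpha 0.05, 80% power, 15% loss). A pooled two-proportion calculation gives 57 evaluable per arm, and 57/0.85 rounds up to 68, within 2 of 66. Conversely, 66 × 0.85 = 56 evaluable per arm, with power 0.798. I use 56 below only as the number likely to be evaluable.

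**Share of the window before randomisation.** With look-back L = 180 days and visit day t, share = max(0, L − t)/L.
- Day 75 (earliest): 105/180 = 58%
- Day 90 (nominal): 90/180 = 50%
- Day 120 (latest): 60/180 = 33%

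Taking six months as 182.5 days gives 59%, 51% and 34%. At the six-month assessment (section 6.6: two weeks early to 30 days late), the share is 0% at the nominal time. At about day 166 it is 14/180 = 8%, or 16.5/182.5 = 9%.

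**Any STI (yes/no).** Let a be the risk in the pre-randomisation part, the same in each arm, and q the risk afterwards. The observed risk is 1 − (1 − a)(1 − q). The risk difference, which is the plan's measure for binary outcomes (section 2.2), is therefore the true difference multiplied by (1 − a). The risks below are assumptions, because the documents give none. They take a day-90 visit and equal risk before and after randomisation in the control arm.
- Three-month risk 10%: 90% of the difference is kept
- 20%: 80% is kept
- 30%: 70% is kept

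Worked case: risk 20%, truly halved to 10%.
- Counting from randomisation: 20% v 10%, difference 0.10.
- Six-month look-back: 1 − 0.8 × 0.8 = 36% v 1 − 0.8 × 0.9 = 28%, difference 0.08.

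Power = Φ{[d√n − 1.96√(2p̄(1 − p̄))]/√[p₁(1 − p₁) + p₂(1 − p₂)]}. With n = 56 it is 0.31 in the first case and 0.15 in the second. If entry selection doubled the pre-randomisation risk to 40% (again an assumption), the contrast would be 52% v 46%, with 60% of the difference kept and power 0.09.

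**Retention in care.** The plan does not say whether the endpoint is a count or a proportion.
- *Missed/scheduled proportion.* With equal numbers of visits scheduled before and after, a control proportion p and a true relative reduction r, the observed difference is p − [p + p(1 − r)]/2 = pr/2, half the true difference pr.
- *Raw count of missed visits.* The earlier visits balance in expectation, so the difference in means is unchanged but the variance grows. For illustration, take Poisson counts with mean 1.0 per three months, truly halved, and 56 per arm. The difference is 0.5 either way. Its standard error rises from √(1.5/56) = 0.164 to √(3.5/56) = 0.250, and power falls from 0.86 to 0.52.

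**The case against.** The strongest reply is that no three-month model is specified for either outcome. The RCT Secondary Analysis Plan fits its binomial model at six months, named as the main time point for CAI, and its mixed models cover five disclosure scales. STIs and retention appear in no specified model and in none of the section 2.3 hypotheses. That stands: the effect falls on any three-month estimate that is made, not on a named analysis. It does not remove the point, because section 10.1.3 has STI infections assessed at three months within the efficacy panel.

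Several stronger readings are tempting, and the documents do not support them.
- *Half of the events counted are pre-randomisation.* The 50% is a share of time. It becomes a share of events only if rates are equal before and after, and no rates are given. The size of the group entering only through an STI is also unknown, since an episode of anal sex qualifies on its own.
- *A halving of the STI rate would look like a reduction of only a quarter.* That is roughly right for a rate ratio under equal rates, but the plan measures differences in proportions, where the loss is smaller.
- *Every effect is biased toward none.* This is not so for a raw missed-visit count, whose expected difference is unchanged. The extra events also create no spurious difference, because they balance across arms in expectation.
- *Events are double-counted.* An STI in the first three months does fall in both follow-up windows, but that double-counts only if visits are summed, and no section sums them.

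One might also read a new diagnosis as one made since the last visit. The text does not say so, and the CASI wording is not in the documents.

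**Conclusion.** The point holds for the three-month assessment of STIs and retention in care. The stated look-back puts half of the window before randomisation at day 90, and 33-58% across the permitted visit days. That share follows from the documents alone.

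The cost in estimation is moderate and rests on assumed rates. An any-STI risk difference keeps about 70-90% of its size for three-month risks of 10-30% that are equal before and after randomisation, and less if entry selects for recent STIs. Power, already low for such an outcome, roughly halves in the 20% illustration. A missed/scheduled proportion loses about half of its difference, while a raw count loses precision only.

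The primary outcome is unaffected. The six-month assessment and CAI are nearly so. Priority is low to moderate, and mainly for STIs: sections 2.2 and 10.1.3 treat them as an efficacy outcome, whereas Table 2 does not. Retention is not named in either section.

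**What to change.** - **Three months.** Count only STI diagnoses and scheduled or missed visits since randomisation. Reword both CASI items to ask about the time since enrolment, and use diagnosis dates for any chart-abstracted STIs. Retention has no chart source in Table 2, so it depends on the survey wording. The three-month abstraction described in sections 5.1 and 6.5 covers viral load only, so the plan should say whether STI dates are abstracted then.
- **Six months.** Count since randomisation for a cumulative outcome, or since the last assessment for separate intervals. State which, and do not sum overlapping windows.
- **Baseline.** Keep the six-month look-back.
- **Table 2.** State whether the retention endpoint is a count or a proportion, and align the status of STIs with sections 2.2 and 10.1.3.

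Counting from randomisation is better than a fixed 90-day recall, which would still reach back 15 of 90 days (17%) at a day-75 visit and would miss the first 30 days at a day-120 visit.

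The cost is two survey items and a line or two of analysis-plan text. The downside is that post-baseline recall no longer matches baseline in length. The survey change should come before further three-month surveys are completed, because a six-month retention answer cannot be split afterwards.
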